3.4 Secondary Efficacy Endpoints

Secondary efficacy endpoints include the following:

- Adequate relief of abdominal pain two weeks after the end of treatment phase and at quarterly intervals through 12 months
- Adequate relief of bowel problems two weeks after the end of treatment phase and at quarterly intervals through 12 months
- Change from pre-treatment baseline of lower GI function (i.e. stool frequency; stool consistency; severity of urgency, bloating and straining) to post-treatment, and at quarterly follow-ups
- Change from pre-treatment baseline in ratings of (a) severity of abdominal pain/discomfort and (b) global severity of IBS symptoms to post treatment and at quarterly follow-ups
- Change from pre-treatment baseline in indices of health related quality of life to post treatment, and at quarterly follow-ups
- The percent of participants who describe themselves as satisfied with assigned treatment at 2-week follow-up using the Client Satisfaction Scale.
- Change from pre-treatment baseline in psychological well-being (e.g. overall mental well-being and discrete emotional problems such as anxiety, depression, somatization) to post treatment, and at quarterly follow-ups

- Change from pre-treatment baseline in health care use to post-treatment, and at quarterly follow-ups
- Gains in estimated quality adjusted life years (QALYs) from pre- to post-treatment
- Change from pre-treatment baseline in extraintestinal symptoms to post-treatment, and at quarterly follow-ups
- The percent of participants responding positively to treatment as measured by the adequate relief of pain and adequate relief of bowel symptoms
- The percent of participants who report adequate relief, improved symptoms, and clinically significant reduction of IBS symptoms by week four (rapid response)
- Safety as measured by the occurrence of adverse events

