APPENDIX 4: Eligibility Criteria

Inclusion Criteria
Gender: male or female
Ages 18-70 years (inclusive)
All ethnic groups
Meet Rome III criteria for IBS
 Moderate to severe IBS symptoms (symptom frequency ≥ 2 days/wk)
Ability to understand and provide informed consent
• With the exception of antibiotics, participant is willing to remain on a stable dose throughout the 4-week pretreatment baseline period prior to randomization
 Participant either not taking medications or if taking medications willing to suspend starting any new medications during the initial 4-week pre- treatment baseline period
A minimum 6 th grade reading level based on the Wide Range Achievement Test (WRAT 4) if necessary
• Participant is willing to be randomized to CBT or Support/Education to which s/he has been assigned and to adhere to protocol requirements
 Participant is willing to attend regularly scheduled therapy sessions during active phase of the trial
 Participant is willing to be contacted and scheduled for follow-up assessments at week 12 and 3, 6, 9, and 12 months after the conclusion of acute treatment phase
 Participant is able to a maintain daily symptom diary and complete questionnaires through treatment and at regularly scheduled follow ups
Participant has access to a telephone
Participant is willing and able to provide adequate information for locator purposes

	Exclusion Criteria
•	Evidence of current structural or biochemical abnormalities or medication use that better explain the participant's IBS symptoms (e.g. IBD)
•	Evidence of a current infection or infection of any type within the 2 weeks prior to the study gastroenterologists' evaluation which would obscure the presentation of IBS symptoms. In such cases the baseline can be delayed until 2 weeks after complete recovery
•	Participant has received antibiotics (e.g. rifaximan and/or neomycin) specifically targeted to treat IBS symptoms. In this instance, eligibility will be suspended for 12 weeks from the initial date the antibiotic was consumed
•	Participant has undergone previous abdominal surgery that would have caused significant alteration of the anatomy/physiology of the digestive/GI tract, which adequately explains GI symptoms
•	Participant has been diagnosed and/or treated for malignancy in the past 5 years with exception of localized basal or squamous cell carcinomas of the skin

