Examples of noncompliance arise if a participant fails to attend two consecutive MC-CBT or S-CBT sessions, or three consecutive EDU sessions without a reason deemed appropriate by his or her therapist and site PI. Non-compliance with homework is not regarded as an acceptable basis for withdrawal.

4. **Administrative error** — Participants who do not meet all study inclusion or exclusion criteria may enter the study in error.

For example, a participant who does not disclose concurrent targeted psychotherapy for IBS or the presence of a medical condition that makes it unsafe or impractical for the participant to continue may be withdrawn at the PI's discretion. These participants may be replaced because they would not have satisfied eligibility criteria had the participant fully disclosed information regarding health status at the time eligibility was determined.

			Page 1 of 2
DATA COLLECTI	ON FORMS S	CHEDULE	00-00-00
ST	UDY IBSOS1 BOOK 1		
NOTE: The columns are marked with an "X" to indicate data and evaluation	ns required at each visit.	PRE-TREATMENT BASELINE	PREMATURE DISCONTINUATION
eData/HAND-ENTERED FORMS	Frontier Form #/ Reference		
IBS0S1 Study Participant Intake Form	QLW01	×	
IBS - Symptom Severity Scale	QLW03	×	
TEV- BL	QLW10	×	
IBSOS Comorbid Disease Form	QLW13	×	
MD Rating - Baseline	QLW15	×	
Concomitant Medications/Supplements and Non-Drug Therapies	CMW1	×	
IBS Module (IBS-PRO)	QLW14	×	
IBSOS1 Study Participant Economic Form	QLW06	×	
FMBS	QLW12	×	
Euroqol EQ- 5D	QLW02	×	
Adverse Events	IBS0021		×
Off Study / Drop Out	IBS1601		×
Missed Visit	ST0010		
Death Form	SP1411		
FLIPS FORMS	Frontier Form #/ Reference		
IBS - LOC	ibsloc	×	
IBS SE Questionnaire	ibsse	×	
bSS	bss	×	
PCSQ-2 Item	pcsq2	×	
IBS-QOL Instrument	ibsqol	X	
McGill - SF	mcgsf	×	
The SF - 12 Health Survey	sf12	×	
Restorative Activities	restact	×	
SOMS-7	soms7	×	
ASI	asi	×	
NSI	vsi	X	
Continued on page 2.			

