APPENDIX 7: Data Collection Schedule

			Page 2 of 2
DATA COLLECTIC	DN FORMS S JDY IBSOS1 BOOK 1	CHEDULE	00-00-00
NOTE: The columns are marked with an "X" to indicate data and evaluation:	s required at each visit.	PRE-TREATMENT BASELINE	PREMATURE DISCONTINUATION
FLIPS FORMS (continued)	Frontier Form #/ Reference		
DIS	dis	×	
PSWQ-A	pswda	×	
ER	er	×	
BDI-II	bdiii	×	
BSI-18	bsi18	×	
STAI-SF	staisf	×	
K-ESS	kess	×	
ISEL-12	isel12	×	
IIP-32	iip32	×	
NIS	nis	×	
TSRQ (A)	tsrqa	×	
Non-Form Evaluation (Exported to Database)			
MINI International Neuropsychiatric Exam Plus	mini	×	
Site-Use Only forms (Not Entered into Database)			
Health Care Coverage f Form		×	
Locator Form		×	

										_	Page 1	of 2
DATA COLLEC	TION FOI	RMS	0)	SCH	Ш		щ				00-00	00-(
STUC	 0Y IBSOS1 - B	OOK 2	~									
NOTE: The columns are marked with an "X" to indicate data and evaluations required at each visit.		Clinic Visit 1	2	OBT and Tel. /isit 1		leation Slinic Isit 2	al Su v	pport T Tel. isit 2	reatme Clinic Visit 3	2 건	inic sit 4	
					5 C	:BT - T	reatm	ent			•	REM.
	Veeks →	1	2	3	4	5	6	7	8	6	10 [ISC.
eData/ HAND-ENTERED FORMS	Frontier Form #/ Reference											
IBS - Symptom Severity Scale	QLW03				_	×				-		×
IBSOS Comorbid Disease Form	QLW13											×
Concomitant Medications/Supplements and Non-Drug Therapies	CMW1	×	×	×	×	×	×	×	×	×	×	×
IBS Module (IBS-PRO)	QLW14											×
IBSOS1 Study Participant Economic Form	QLW06											×
FMBS	QLW12											×
Euroqol EQ-5D	QLW02											×
IBSOS Daily Diary	LGW1	×	×	×	×	×	×	×	×	×	×	×
IBSOS1 Study Participant Follow Up Form	QLW17											×
LEV-FU	QLW11											×
MD Rating- Follow Up	QLW16											×
Adverse Events	IBS0021											×
Off Study / Drop Out	IBS1601											×
Missed Visit	ST0010											
Premature Discontinuation of Study Treatment	IBS4000											
Death Form	SP1411											
FLIPS FORMS	Frontier Form #/ Reference											
BS - LOC	ibsloc	×		×		×			×			×
IBS SE Questionnaire	ibsse	×		×		×			×			×
bSS	ssd	×		×		×			×			×
PCSQ-2 Item	pcsq2	×		×		×			×			×
IBS-QOL Instrument	ibsqol		_									×
McGill - SF	mcgsf		_									×
The SF - 12 Health Survey	sf12		-		_		_			_		×
Restorative Activities	restact		_		_		_	_		_		×
Continued on page 2.												

										Pag	e 2 of 2	
DATA COLLEC	TION FO	RMS 300K 2	S	CH	B	Ч	ш			00	00-00-	
NOTE: The columns are marked with an "X" to indicate data and evaluations required at each visit.		Clinic	v	BT and Tel.	Cli	ationa	Tel.	ort Treatm Clinic	Jent	Clinic		1

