The McGill Pain Inventory-Short Form ⁶³ will measure pain sensation, pain affect, and current pain intensity at each of the 6 assessment periods. The main component of the SF-MPQ consists of 15 descriptors (11 sensory, 4 affective) that participants rate on a 4-point intensity scale (0 = none, 1 = mild, 2 = moderate, 3 = severe). Three pain scores are derived from the sum of the intensity rank values of the words chosen for sensory, affective, and total descriptors. The SF-MPQ scores obtained from participants in postsurgical and obstetrical wards and physiotherapy and dental departments were compared to the scores obtained with the standard MPQ. The correlations were consistently high and significant. The SF-MPQ was also shown to be sufficiently sensitive to demonstrate differences due to treatment at statistical levels comparable to those obtained with the standard form. The SF-MPQ is a useful measure for studies or clinics in which the standard MPQ would require too much time to administer. We will also assess the intensity (worst, average) of pain/discomfort on a daily basis using an 11-point Numerical Rating Scale (where 0 = none, 10 worst imaginable). Respondents will rate the intensity of other types of unpleasant visceral sensations (e.g. bloating, urgency) using similar numerical ratings scales embedded in GI Diaries.

Somatization

The seven day version of the **Screening for Somatoform Symptoms** (SOMS-7) ⁶⁴ is a self-rated checklist that assesses the severity of 53 unexplained medical symptoms. The questionnaire includes all 33 physical complaints of the DSM-IV somatization disorder symptom list, the symptoms of ICD-10 somatization disorder, and the ICD-10 somatoform autonomic dysfunction symptom list. Participants are asked whether they had experienced the listed physical symptoms during past seven days. They were instructed only to describe rate the degree of impairment for medical symptoms for which "*no clear causes have been found by physicians and which have affected your well-being*". The SOMS-7 measures somatization and therefore has conceptual and psychometric advantages over self described "somatization" measures (e.g., PHQ-15) that assess severity of somatic symptoms⁶⁵

Altered Bowel Function

Stool consistency

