Per Rome III guidelines ⁶⁶, the seven-item **Bristol Stool Consistency Form** ⁶⁷, will be used to characterize the consistency (form) of participants' stool. Information from the Bristol Stool Form will subtype IBS type by predominant stool pattern at baseline and post treatment assessment periods. The Bristol Stool Scale is regarded as a surrogate marker of gastrointestinal transit time with stool type 1 or 2 defined as slow colonic transit; stool of type 3-5 defined as normal colonic transit; and stool of type 6 and 7 defined as fast colonic transit.

Stool frequency

We will also measure the frequency of bowel movements (BM), spontaneous bowel movements (SBM) and complete spontaneous bowel movements (CSBM) compared to baseline ⁶⁸. An SBM is a bowel movement that occurs in the absence of laxative, enema or suppository usage within the preceding 24 hours. A CSBM is operationalized as an SBM (i.e., BM without use of laxative, enema or suppository usage within the preceding 24 hours) that is accompanied by a feeling of complete evacuation. The frequency of bowel movements will be measured at baseline, daily during the acute treatment phase, and for the two weeks before each post treatment follow-ups.

Health-Related Quality of Life (QOL)

We will be administering four questionnaires to assess discrete dimensions of quality of life ⁶⁹⁻⁷². The psychometric properties of the proposed QOL measures are well established ⁶⁹⁻⁷².

Generic QOL

The **SF-12 v2 Health Survey** ⁷⁰ is an abbreviated (12-item) version of the SF 36 generic quality-of-life instrument. The SF 12 contains one or two items that measure each of the eight domains included in the SF-36: physical functioning, role limitations resulting from physical health, bodily pain, general health perceptions, vitality, social functioning, role limitations resulting from emotional problems, and mental health. It yields scale scores for each of these eight health domains and two summary measures of physical and mental health, the Physical Component Summary (PCS) and Mental Component Summary (MCS). Subscale scores yield two summary scores: Physical Component Summary (PCS) and Mental Component Summary (PCS) and Mental Component Summary (PCS) and Mental Component Summary (MCS) scales. Scores are transformed to have a mean value of 50, standard deviation (SD) 10, where scores above or below 50 are above- or below-average physical or mental well-being, respectively

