- Interim assessment Participants will describe their daily bowel habits using the Bristol Stool form and rate the intensity of pain, bloating, and urgency (11-point VAS) at the end of each day through the 10-week acute treatment phase. At the end of each week of the acute treatment phase, they will rate global symptom severity, satisfaction with IBS symptoms, life interference, and mood using the abbreviated POMS, and time spent completing homework assignments. In addition, participants will complete process measures (IBS SE, WAI, IBS LOC, etc) at regularly scheduled times during active treatment phases. Participants should complete process measures within seven days of their being assigned.

- Two-week follow-up assessment The two-week assessment should occur two weeks from the date of the last active treatment session, plus or minus (+) two weeks.
- Three-month assessment The three-month assessment should occur three months ± two weeks from the date of the last active treatment session.
- Six-month assessment The six-month assessment should occur six months \pm two weeks from the date of the last active treatment session.
- Nine-month assessment The nine-month assessment should occur nine months ± two weeks from the date of the last active treatment session.
- 12-month assessment The 12-month assessment should occur 12 months \pm two weeks from the date of the last active treatment session.

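### The Book 1 baseline schedule omits the daily diary, although the pain and CSBM responders and Appendix 8 call for pre-treatment values

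*Protocol*

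**What the plan says.** **Schedule (Appendix 7).** Book 1 covers the column headed "PRE-TREATMENT BASELINE". Its hand-entered forms run from the EQ-5D straight to Adverse Events, and neither its questionnaire list nor its site-use list contains a diary. Book 2 has a row for the "IBSOS Daily Diary" (LGW1), marked for weeks 1 to 10. Book 3 has the same row, marked at all five follow-ups.

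**Text on timing.** For stool frequency, Appendix 8 says: "The frequency of bowel movements will be measured at baseline, daily during the acute treatment phase", and adds the two weeks before each follow-up. For stool form it says: "Information from the Bristol Stool Form will subtype IBS type by predominant stool pattern at baseline". For pain it says: "We will also assess the intensity (worst, average) of pain/discomfort on a daily basis using an 11-point Numerical Rating Scale", without naming a baseline period. The interim-assessment entry places the daily stool, pain, bloating and urgency ratings "at the end of each day through the 10-week acute treatment phase". The inclusion criterion in Appendix 4 requires that a participant can "maintain daily symptom diary and complete questionnaires through treatment and at regularly scheduled follow ups".

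**Endpoints.** Section 3.4 includes "Change from pre-treatment baseline of lower GI function (i.e. stool frequency; stool consistency; severity of urgency, bloating and straining"). The text that follows it defines the weekly responder by improvement from before treatment, with components in 3.5 to 3.7. Sections 7.3 and 7.4 use the baseline score as covariate. Section 2 provides four weeks of baseline data collection before randomization.

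**The concern.** The diary is the form that would carry daily worst pain, daily bloating and urgency, and day-by-day bowel movement counts. The baseline book is the one book that leaves it out, yet several endpoints are defined against a pre-treatment level. A site that works from the form schedule would collect no pre-treatment weekly average of worst pain and no pre-treatment CSBM count.

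An analysis plan cannot repair this. Pre-treatment diary days cannot be recovered once therapy has begun, and the first diary week on the schedule, week 1, is after allocation and is the week of the first clinic visit.

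**Working it through.** No figure in the protocol bears on this point, so the check sets the schedule against the definitions.

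**Step 1: diary marks in Appendix 7**

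| Book | Period | Diary (LGW1) |
|---|---|---|
| 1 | Pre-treatment baseline | no row |
| 2 | Treatment weeks 1–10 | 10 of 10 |
| 3 | Follow-up | 5 of 5 |

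In Books 2 and 3 the diary row comes directly after the EQ-5D row. In Book 1 the row after the EQ-5D is Adverse Events. A whole row is absent, which a lost mark in a badly reproduced table would not explain.

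**Step 2: what each definition needs**

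Let P0 and C0 be the pre-treatment weekly average of worst pain and weekly CSBM count, and Pk and Ck their values in week k.

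- Pain (3.5): (P0 − Pk)/P0 ≥ 0.30. Needs P0.
- Stool frequency (3.6): Ck − C0 ≥ 1. Needs C0.
- Stool consistency (3.7): weekly average Bristol type ≤ 5. Needs no baseline.
- Change in stool frequency, urgency and bloating (3.4): needs a pre-treatment value of each.

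Two of the three responder components therefore need a baseline. The constipation responder combines pain and stool frequency; the diarrhoea responder combines pain and stool consistency. Both composites depend on P0.

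**Step 3: does the text supply the baseline where Book 1 does not?**

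- Stool frequency and stool form: yes in intention. Appendix 8 commits to a baseline measure of each, but names neither the form nor the number of days.
- Daily worst pain, bloating and urgency: no text examined states baseline collection.

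**Step 4: can another Book 1 form stand in?**

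- The McGill short form gives descriptor scores and current pain, not a weekly average of daily worst pain on a 0–10 scale.
- The IBS-SSS and IBS-PRO, both in Book 1, cover pain, distention, altered defecation, bloating and urgency in summary. As described, they give neither a weekly average of daily worst pain nor a CSBM count.
- By the Appendix 8 definition, a CSBM requires knowing, for each movement, about laxative, enema or suppository use in the preceding 24 hours and whether evacuation felt complete.

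**Step 5: precision, as an assumption only**

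If a continuous diary outcome lost its baseline covariate, its residual variance would rise by the factor 1/(1 − r²), where r is the baseline–outcome correlation. The protocol gives no r. For assumed values:

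- r = 0.3: 1/(1 − 0.09) = 1.10
- r = 0.5: 1/(1 − 0.25) = 1.33
- r = 0.7: 1/(1 − 0.49) = 1.96

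This applies to continuous outcomes analysed by covariance, not to the binary responders in 3.5 and 3.6.

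**The case against.** The best counter-argument is that omission from one table does not show that the data are not collected.

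- Section 2.1 refers to Appendices 1 and 2 for the overview and work flow. Their text was not available for checking and may describe a baseline diary. This stands: absence from the whole plan cannot be shown. It would not clear Book 1, which would then conflict with those appendices as well.
- Appendix 7 does not list every planned measure; the CDC HRQOL-4 described in Appendix 8 has no row of its own. This carries less weight for the diary, which has its own row and form number in the other two books.
- The interim-assessment entry concerns the treatment phase and is silent on the follow-up diary too, so its silence on baseline excludes nothing. The inclusion criterion describes what a participant must be able to do and is not a collection schedule. Both points stand: these texts fail to supply a baseline diary but do not rule one out.
- The lower-GI endpoint in 3.4 does not name the diary as its instrument, and the IBS-PRO and IBS-SSS touch the same symptoms at baseline. This stands in part: those symptoms have some baseline measure, but worst pain and CSBM are not replaced.

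A reader might infer that every diary-based endpoint loses its reference value. The documents do not support that: Appendix 8 intends baseline stool frequency and form, and the stool-consistency component is an absolute threshold. A reader might also infer that treatment week 1 would serve as the baseline. Nothing in the protocol says so; it is only the earliest diary week on the schedule.

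**Conclusion.** The schedule and the text disagree, and this should be corrected. Book 1 omits the diary, while Appendix 8 and Sections 3.4 to 3.6 presuppose pre-treatment values. If Book 1 is followed as written and no other document adds a baseline diary, the listed forms give no pre-treatment weekly worst-pain or CSBM value. Both interim composite responders are then affected, because each includes the pain component. The gap is clearest for daily worst pain, bloating and urgency. For stool frequency and form, a baseline is planned and only the form and window are missing.

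The primary endpoint, global improvement, is untouched, so this is a matter for secondary and interim endpoints. No firm numerical loss can be given: the variance factor of 1.10 to 1.96 rests entirely on an assumed correlation of 0.3 to 0.7.

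**What to change.** 1. Add LGW1 to Book 1, within the four-week baseline period that already exists.
2. State the baseline window for weekly average worst pain and for weekly CSBM. The last two weeks before randomization would be one option, matching the two-week window that Appendix 8 sets for stool frequency before each follow-up.
3. In Appendix 8, name the form that supplies baseline stool frequency and stool form, and say that the daily pain, bloating and urgency ratings are also taken at baseline. Bring the interim-assessment entry and the diary inclusion criterion in Appendix 4 into line.
4. If Appendix 1 or 2 already provides for a baseline diary, correct Book 1 to match it.

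The cost is a schedule amendment using an existing form in an existing period, plus some diary burden for participants before randomization. It has to be done before participants start therapy, since the missing days cannot be collected afterwards.

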2. STUDY SCHEDULE AND TIMELINE

IBSOS is a prospective, randomized, multi-site clinical trial comparing three types of psychotherapy delivered in an individual format for severely affected adults with IBS. After a four-week baseline data collection period, participants will be randomly assigned to receive either four-session self-administered CBT, 10-session therapist-administered CBT or a control condition emphasizing support and education (allocation 1:1:1). The acute treatment phase will last 10 weeks. Participants will undergo follow-up examinations two weeks after treatment ends (week 12) and three, six, nine, and 12 months after the end of treatment.

IBSOS requires the expeditious enrollment of a sufficient number of participants to ensure the statistical power and generalization of study results. This trial plans to recruit 480 participants over an approximately four-year treatment delivery period. Assuming a relatively conservative pre randomization dropout rate of 25%, each site will need to phone telephone screen approximately 150 participants per year and enroll (consent) 75 in order to meet yearly recruitment quotas of 60 randomized participants at each site.

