		Visit 1	>	isit 1	FC-CE	і:2 T-Tr	Visit eatmen	2 Visit	~	Visit 4	PREM	· · ·
	Veeks →	1	5	3	4	9	7	8	6	10	DISC.	-
FLIPS FORMS (continued)	Frontier Form #/ Reference											
2-SWOS	soms7		_			_			_		×	-
ASI	asi	×	-	×				×			×	
NSI	vsi	×		×		~		×			×	
DIS	dis	×		×		~		×			×	
PSWQ-A	pswga	×		×		~		×			×	 
ER	er	×		×				×			×	-
BDHI	bdiii										×	-
BSI-18	bsi18										×	
STAI-SF	staisf										×	
K-ESS	kess										×	
ISEL-12	isel12										×	
IIP-32	iip32										×	
NIS	nis										×	
WAI-SR-PATIENT	waisrpt	×		×	^	~		×			×	
WAI-SR-THERAPIST	waisrth	×		×		~		×			×	
ATT	QLW1	×	_									
IBS Treatment Suitability and Patient Expectation Form	patexppt	X										
IBS Treatment Suitability and Patient Expectation Form Therapist Version	patexpth	×										
Homework Compliance Form	hwcf	 	K	×	×	×	×	×	×	×		_
Adequate Relief	adgrel					~					×	
Global Impression of Change	gloc					~					×	
TSRQ (B)	tsrqb		_			~					×	
Client Satisfaction Questionnaire4	csq		\neg	_	_	_			_		×	-1
Site-Use Only forms (Not Entered into Database)												
Locator Form			_						_			-

							Page 1 of 2
DATA COLLE	ECTION FOI STUDY IBSOS1 - B	RMS 00K 3	SCI	HED	ULE		00-00-00
NOTE: The columns are marked with an "X" to indicate			FOLLO	W-UP PE	RIODS		
data and evaluations required at each visit	Months →	٦	3	9	6	12	Premature
	Weeks →	12	22	34	46	52	Discontinuation
eData/ HAND-ENTERED FORMS	Frontier Form #/ Reference						
IBS - Symptom Severity Scale	QLW03	×	×	×	×	×	×
IBSOS Comorbid Disease Form	QLW13	×	×	×	×	×	×
Concomitant Medications/Supplements and Non-Drug Therapies	CMW1	×	×	X	×	×	X
IBS Module (IBS-PRO)	QLW14	×	×	×	×	×	×
IBSOS1 Study Participant Economic Form	QLW06	×	×	×	×	×	×
FMBS	QLW12	×					×
Eurodol EQ-5D	QLW02	×	×	×	×	×	×
IBSOS Daily Diary	LGW1	×	×	×	×	×	×
IBSOS1 Study Participant Follow Up Form	QLW17	×	×	×	×	×	×
LEV-FU	QLW11	×	×	×	×	×	×
MD Rating- Follow Up	QLW16	×	×	×	×	×	×
Adverse Events	IBS0021						Х
Off Study / Drop Out	IBS1601						×
Missed Visit	ST0010						
Premature Discontinuation of Study Treatment	IBS4000						
Death Form	SP1411						
FLIPS FORMS	Frontier Form #/ Reference						
IBS - LOC	ibsloc	×	х	х	x	×	×
IBS SE Questionnaire	ibsse	×	×	×	×	×	×
PSS	ssd	×	×	×	×	×	×
PCSQ-2 Item	pcsq2	×	×	×	×	×	×
IBS-QOL Instrument	ibsqol	X	Х	Х	Х	×	×
McGill - SF	mcgsf	×	X	X	X	×	×
The SF - 12 Health Survey	sf12	×	×	×	×	×	×
Restorative Activities	restact	×	×	×	×	×	×
SOMS-7	soms7	×	×	×	×	×	×
Continued on page 2.							

Page 44 of 67

							Page 2 of 2	

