The abbreviated version of the original **Coping Strategies Questionnaire** ^{96 97} will be used to assess the frequency of use each of six cognitive coping strategies and one behavioral strategy when one feels pain: diverting attention, reinterpreting pain sensations, ignoring pain, praying and hoping, coping self-statements, increasing behavioral activities, and catastrophizing. Of particular interest is the pain catastrophizing scale as pain catastrophizing is associated with greater pain and functional limitations in participants with a range of persistent painful medical disorders including IBS ⁹⁸⁻¹⁰¹. The two items of the catastrophizing subscale ask participants to rate the frequency with which they, during an episode of pain, engage in various beliefs thought to index catastrophizing (e.g. "When I am in pain, I feel I can't stand it anymore," "It's awful and I feel it overwhelms me"). Respondents rate how characteristic each item is of them using a six-point Likert scale (0 = never do, 6 = always do).

Treatment Expectancies

At the end of session 1, participants' expectancies that they will respond successfully to treatment will be measured using the **Expectation of Improvement/Treatment Suitability Form** ^{102, 103}, asking "Which of the following best describes how successful you think your treatment will be?" Responses are rated using an 11-point visual analog scale (0 = not at all, 10 = completely). The form's second question ("How suitable do you think your treatment will be for your IBS symptoms?") measures suitability of treatment. In consultation with behavioral treatment efficacy expert [name], we developed a therapist version of the form that requires clinicians to rate their estimation of the suitability of their participants' assigned treatment and the likelihood that treatment will be successful as a way of assessing potential allegiance effects ¹⁰⁴, an important nonspecific variable whose role in shaping outcomes has received scant attention by clinical researchers. The therapist version of the treatment suitability questionnaire should be completed before randomization to minimize the extent to which treatment allocation shapes judgments of suitability.

Therapeutic Alliance

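### Appendix 8 wants the therapist suitability form done before randomization, Appendix 7 schedules it in treatment week 1, and its described content presupposes an assigned arm

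*Protocol*

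**What the plan says.** Three places in the protocol bear on this.

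- **Appendix 8, Treatment Expectancies, on content and purpose.** The therapist form "requires clinicians to rate their estimation of the suitability of their participants' assigned treatment and the likelihood that treatment will be successful", and it does so "as a way of assessing potential allegiance effects". The appendix calls this an important nonspecific variable that has been little studied.
- **Appendix 8, same paragraph, on timing.** "The therapist version of the treatment suitability questionnaire should be completed before randomization to minimize the extent to which treatment allocation shapes judgments" of suitability.
- **Appendix 7, Data Collection Schedule.** The row "IBS Treatment Suitability and Patient Expectation Form Therapist Version" (patexpth) stands in Book 2, which covers the treatment weeks. It has a single mark, in the column for Clinic Visit 1, week 1. The form is listed neither in Book 1 (pre-treatment baseline) nor in Book 3 (follow-up).

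Section 2 fixes the order of events: "After a four-week baseline data collection period, participants will be randomly assigned to receive" one of the three treatments. Section 5.1 says that the assignment comes from a web-based system.

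**The concern.** The form is there to capture how much the therapist believes in a treatment for a given participant. In a psychotherapy trial whose participants cannot be blinded, that belief is a rival explanation for an advantage of CBT over the attention control. The protocol sees that a rating made with knowledge of the arm is contaminated by it, and asks for the rating beforehand for that reason. The schedule puts it afterwards.

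A rating of the assigned arm made after allocation can differ between arms because of the allocation itself. It then no longer separates the therapist's prior belief from the reaction to the assignment. A rating from before allocation cannot be recovered later if it was not taken.

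**Working it through.** No arithmetic is needed to establish the conflict; the check is a comparison of passages.

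**Step 1: where the form appears.** Reading the rows of all three books in Appendix 7:

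| Book | Period | Entries for patexpth |
|---|---|---|
| 1 | Pre-treatment baseline | 0 |
| 2 | Treatment, weeks 1 to 10 | 1 (week 1) |
| 3 | Follow-up | 0 |

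**Step 2: is week 1 after randomization?** Yes. By Section 2, randomization follows the four-week baseline and determines which treatment is received, so the first treatment visit comes after it.

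**Step 3: could the column be misread?** The table is damaged in the text available, but the conclusion does not depend on the exact column. Every column of Book 2 is a treatment week or premature discontinuation, so any position in that book is after allocation. The patient version, which Appendix 8 places at the end of session 1, carries the same single mark. The two forms appear to have been scheduled as a pair.

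**Step 4: can the form as described be completed at the time the text asks for?** The described content refers to the assigned treatment. Before randomization there are three possible treatments and none is assigned. Moving the form to Book 1 without changing what it asks would therefore leave a second conflict, this one inside Appendix 8.

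**Step 5: what follows for the data.**

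- *All sites follow Appendix 7:* all ratings are post-allocation.
- *All sites follow the timing in Appendix 8:* the ratings precede allocation, but therapists have to guess which treatment the question refers to.
- *The sites differ:* with 240 participants planned at each of two sites (Section 4.1), about half of the 480 ratings would be pre-allocation and half post-allocation. The difference would coincide with site.

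**Step 6: what the rating feeds into.** Sections 7.3 and 7.4 name the baseline score as covariate for the outcome comparisons and do not mention therapist ratings. Aim 3, Hypothesis 2 names therapeutic alliance and positive expectancy of improvement, not therapist allegiance.

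**The case against.** The best defence is that Appendix 8 gives the right instruction, with its reason, and that the schedule row is a clerical slip. The protocol also refers to a Detailed Work Flow (Appendix 2) and a manual of operations. Neither was available for this check, and either may state when the therapist form is completed. The form itself is not reproduced, so its items may differ from the one-sentence description. All of this stands, and it limits the claim to a conflict between instructions.

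Three stronger readings are tempting, and the documents do not support them.

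- *That no participant will have a pre-randomization rating.* This is true only if every site follows Appendix 7 over the explicit text of Appendix 8.
- *That the rating is coloured by the first session.* Appendix 8 places the participant's form at the end of session 1. For the therapist's form, Appendix 7 gives only a visit, not whether it is completed before or after the session.
- *That adjusting for the rating would remove real treatment effect.* No such adjustment is planned.

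It can also be said that an exploratory process measure deserves no more than a minor note. That is right about the reach of the problem. It does not remove the fact that a site cannot obey both appendices, or that the lost rating cannot be collected later.

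**Conclusion.** The point holds as an inconsistency with a real but narrow consequence. Appendix 7 and Appendix 8 disagree on when the therapist form is completed, and the content described in Appendix 8 does not fit the timing that it asks for. Under Appendix 7 the rating is a post-allocation variable and cannot serve as the allegiance measure the protocol describes. Under mixed practice its meaning varies by site.

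The consequence stops at this one process measure. The primary endpoint, the sample size, the error rates and the planned covariate adjustment do not depend on it. The conclusion assumes that the described content reflects the actual form, and that no operational document already settles the timing. It should be corrected, because the documents as they stand do not reliably deliver the measure they set out to collect.

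**What to change.** - **Schedule.** List patexpth in Book 1 of Appendix 7, to be completed after the baseline assessment and before the web-based randomization.
- **Content.** Reword the form, and its description in Appendix 8, so that the therapist rates suitability and likely success for each of the three treatments for that participant.
- **Data kept.** Retain all three sets of ratings. Allegiance is a preference between treatments, so keeping only the rating for the arm later assigned would discard the comparison that shows it.
- **Week 1.** If a week-1 rating is also wanted, label it as post-allocation and do not use it as the allegiance measure.
- **Consistency.** Bring the Detailed Work Flow and the manual of operations into line, so that both sites do the same.

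The cost is small: one form moved and reworded. Two items for each of three treatments make 2 × 3 = 6 answers per participant in place of 2. The one practical demand is that the therapist be identified before allocation and know enough about the participant from baseline to give a rating.
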